4.4 STUDY DESIGN, TIME AND EVENT SCHEDULE, FLOWCHART

The study will be a bilateral, subject-masked, randomized, 2x2 cross-over, non-dispensing pilot study involving three clinic visits. Investigators who collect measurements for primary and secondary endpoints will also be masked to the identity of the study lenses. The study will have two treatments (Test and Control) in two periods (first and second) with two randomization groups (Test/Control or Control/Test).

The participants will attend a first Enrolment / Fitting visit to initially obtain their informed consent and evaluate the potential participant's suitability to take part in the investigation. If they fulfill the investigation's inclusion and exclusion criteria, they will be enrolled, fitted with the study contact lens type to ensure that a clinically acceptable fit is achieved and trained into the testing procedures. This visit will last for approximately three hours. At the completion of the visit the test and control contact lenses will be ordered. When the study contact lenses become available the participants will then attend two test visits during which one of the study contact lens types will be tested each time. The order of testing of the test or control contact lens will be determined at random. The participants will attend the visits not wearing contact lenses and not having worn contact lenses that day. Each measurement visit will last for approximately 4.5 hours.

The participants will not take part in any concomitant investigation of any type or take concomitant medications not allowed by the exclusion criteria.

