6.	Randomization	Study Lens Type will be selected based on the Randomization Scheme	
7.	Study lens insertion	The initial study contact lenses will be selected based upon the randomization schedule. Place the lenses on the subject eyes.	
8.	Lens Damage	Inspect the lenses on eye with the biomicroscope for damage and if damaged, record the damage and have the subject insert a new lens. Save worn, damaged lenses in sterile saline in the labeled vials provided with the study materials and complete the quality product complaint form.	
9.	Lens Settling	Allow the lenses to settle for at least 15 minutes.	
10.	Spherical Over-Refraction and Visual Acuity	A monocular distance spherical over-refraction will be performed. The distance visual acuity to the nearest letter will be recorded OD, OS and OU.	Manual of Procedures [REDACTED]
11.	Subjective Lens Fit Assessment	
Lens centration, primary gaze movement, upgaze movement and tightness (push-up test) will be evaluated and graded.
 
The subject should not proceed to wear the contact lenses if any of the following is observed:
 
 • presence of limbal exposure (appearance of clear cornea) in any gaze • presence of edge lift • presence of unacceptable movement (excessive or insufficient) in all three movement categories (primary gaze, upgaze, and push-up). 
If either lens is deemed unacceptable, the
	Manual of Procedures [REDACTED]

		subject will be discontinued from the study. Remove the lenses, perform a slit-lamp evaluation, and complete the Final Evaluation form.	
12.	Visual Field Measurement	Esterman visual fields will be measured OD, OS and OU using a Humphrey perimeter.	Manual of Procedures

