13.	Vision Assessments	
Time Controlled Visual Acuity (TCVA) Measurements will be made at 4m using 2.5 and 250 cd/m² luminance, and at 67cm using 50 cd/m² luminance. The luminance requirements will be the same at the target and at the eye. Monocular and binocular visual performance will be measured for the following conditions:
 
 • Distance 2.5 cd/m² 
 ○ Central ○ 5 degrees eccentricity ○ 20 degrees eccentricity • Distance 250 cd/m² 
 ○ Central • Intermediate 50 cd/m² 
 ○ Central ○ 5 degrees eccentricity ○ 10 degrees eccentricity 
The order of luminances tested will be randomized.
 
Subjects will undergo a driving simulation test and subsequently make a subjective assessment of their visual performance.
 
Subjects will play computer based reaction time games and subsequently make a subjective assessment of their visual performance.
	Manual of Procedures
14.	Lens Removal	The contact lenses are removed and discarded.	

15.	Biomicroscopy	
Biomicroscopy will be performed OD and OS. Standard Slit Lamp Classification Scales will be used to grade the findings. For the limbal and conjunctival redness, 0.5 unit increments will be used in the grading.
	
Manual of Procedures
 
16.	Distance Spherocylindrical Refraction and Exit Visual Acuity	An optimal, binocular balanced distance spherocylindrical refraction will be performed. The distance visual acuity to the nearest letter will be recorded OD, OS and OU.	
Manual of Procedures
 
17.	Continuance	Indicate whether the subject will continue to the next visit. If not, proceed to Final Evaluation.	

Visit 3: Second Measurement Visit (2 to 14 days after Visit 2)			
Step	Descriptor	Details	Appendix
1.	Concomitant Medications/Treatments	Questions regarding the subjects' medications and/or treatments.	
2.	Subject Reported Ocular Symptoms	Record any symptoms or problems that the subject may experience with their habitual contact lenses, if applicable. Subject will not be asked about specific categories of complaints, but the severity or frequency will be recorded in the following categories: 
 • Burning/Stinging • Itchiness/Scratchiness • Dryness • Lens Awareness • Grittiness/Foreign Body Sensation • Redness • Irritation/Discomfort • Cloudy/Blurry/Hazy • Variable Vision • Other 	

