8.1 SAFETY PARAMETERS

The following safety parameters will be monitored and evaluated:

- Ocular physiology characteristics
- Lens fitting characteristics
- Adverse events
- Ocular symptoms
- Snellen distance visual acuity
- Reasons for discontinuation
- Reasons for unplanned lens replacement
- Quality Complaints

Safety parameters will be tabulated using frequency distribution tables and descriptive statistics. Adverse events will be listed by subject/eye. There will be separate summary tables for adverse events and infiltrative adverse events. Statistical methods for analyzing safety data, if any, are provided in section 9.

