9.1 STATISTICAL METHODS TO BE EMPLOYED

All data summaries and statistical analyses will be performed using either the SAS software Version 9.4 or higher (SAS Institute, Cary, NC) or SPSS software Version 23.0 or higher (IBM Corp, Armonk, NY).

Description of Summary Tables

Summary tables (Descriptive statistics and/or frequency tables) will be provided for all baseline, efficacy and safety variables for each subject/eye as appropriate. Continuous variables will be summarized with descriptive statistics (n, mean, standard deviation (SD), median, minimum and maximum). Frequency count and percentage of subjects or eyes within each category will be provided for categorical variables.

Summaries will be presented by study lens type and will be performed separately by study population defined in section 9.7. Efficacy variables will be summarized descriptively on both the analysis and safety population. Safety variables will be summarized descriptively for the safety population. Unscheduled visits will be summarized separately if applicable. If the difference between the analysis and safety population is higher than 15%, a sensitivity analysis will be conducted on the safety population.

Data summarization will be performed by OTG-i, with oversight by the JJVCI study responsible biostatistician.

Raw data will be provided to OTG-i by JJVCI/Bioclinica in the Study Data Tabulation Model (SDTM) format in conformance to Clinical Data Interchange Standards Consortium (CDISC) standards. OTG-i will be responsible to create CDISC Analysis Data Model (ADaM) datasets as well as the display outputs including tables, listings and figures (TLFs) based on the CDISC ADaM datasets. For more details about CDISC, SDTM and ADaM, please refer to www.cdisc.org.

OTG-i shall follow specifications of ADaM datasets and mock shells of TLFs provided by JJVCI. Sample datasets, ADaM specifications, and mock shells of TLFs may be provided to OTG-i by JJVCI midway through the study if needed.

Description of Analysis Methods

Efficacy Analysis Set

The primary and secondary analysis will be performed on all randomized subjects who successfully completed the study without any protocol deviations that the study responsible clinician documents as impacting the assessment of the hypotheses (i.e. analysis population). Justification of excluding subjects with protocol deviations in the analysis population set will be documented.

Analysis Methods

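### Ocular symptoms are a safety parameter and summaries are by study lens type, but every visible scheduled symptom record precedes lens insertion and asks about habitual lenses

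*Combined protocol and SAP*

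**What the plan says.** Section 8.1 includes "Ocular symptoms" in its list of safety parameters and continues: "Safety parameters will be tabulated using frequency distribution tables and descriptive statistics". Section 9.1 says that summary tables "will be provided for all baseline, efficacy and safety variables for each subject/eye as appropriate", and then: "Summaries will be presented by study lens type and will be performed separately by study population defined in section 9.7".

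Section 4.7.1 schedules a symptom record at Visit 1 step 6, Visit 2 step 2 and Visit 3 step 2. The instruction is the same each time: "Record any symptoms or problems that the subject may experience with their habitual contact lenses, if applicable". Answers are sorted into listed categories that include dryness, lens awareness, cloudy or hazy vision and variable vision.

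At Visits 2 and 3 the study lens goes in at step 7: "The initial study contact lenses will be selected based upon the randomization schedule". Section 4.4 adds: "The participants will attend the visits not wearing contact lenses and not having worn contact lenses that day".

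**The concern.** The analysis sections lead a reader to expect symptom columns for Test and Control. The visit schedule collects nothing that could fill them. At each measurement visit the symptom question is asked while the subject is wearing no lens, before the study lens is inserted, and it concerns the subject's own lenses.

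Section 3.1 gives the aim as finding out whether the annulus is likely to harm the wearer's vision. A symptom table showing no Test–Control difference could be taken as modest reassurance on tolerability. Built from these records it would carry no such information, because the answers precede the exposure they would be labelled with.

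**Working it through.** The plan states no figure on this point, so the check is one of step order and wording, followed by a simple count.

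**Order of events in section 4.7.1**

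| Visit | Symptom record | Lens placed | Lens removed | Symptom record after wear |
|---|---|---|---|---|
| 1 (fitting lenses) | step 6 | step 15 | step 23 | none |
| 2 | step 2 | step 7 | step 14 | none |
| 3 | step 2 | step 7 | step 14 | none |
| Final Evaluation | none | – | – | none |

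The schedule in section 4.4.1 gives the same order, so this is not a slip in one table. At Visit 2 the symptom record also precedes randomization (step 6).

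**Count of records**

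- Scheduled symptom records per subject: 3.
- Taken before lens placement at that visit: 3 of 3.
- Worded about habitual lenses: 3 of 3.
- Taken during or just after Test or Control wear: 0 of 3.

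**Count of exposures**

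- Cohort target (section 9.2): 20 completers × 2 lenses = 40.
- Enrolment limit (sections 2.6 and 9.2): 25 subjects × 2 lenses = 50, if all wear both. This ceiling suits a safety table better, because the safety population in section 9.7 is not restricted to completers. Section 9.2 allows the limit of 25 to be exceeded by joint agreement.
- Exposures with a scheduled symptom record on the lens: 0 of 40, or 0 of 50.

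**What a by-lens table would contain.** If each step 2 record is labelled with that visit's lens, both columns hold values from before exposure. Apart from carry-over, the expected Test–Control difference is zero whatever the lens does. The Visit 3 record is the only one taken after any Test or Control wear, 2 to 14 days after Visit 2. Any residual effect it caught would belong to the Visit 2 lens but would be tabulated under the Visit 3 lens.

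**Comparison with other safety measures.** Biomicroscopy and refraction with acuity are done before insertion and again after removal: steps 3–4 and 15–16 at Visit 2; steps 3–4 at Visit 3 and steps 1–2 of the Final Evaluation. Symptoms have only the first half of that pattern.

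**The case against.** **Other data are collected on the lens.** At step 13 subjects rate their own visual performance after the driving simulation and after the reaction-time game. Acuity, Esterman fields and the time-controlled acuity tests are also done per lens. This stands. A reader might infer that visual complaints on the study lens go wholly unrecorded, and the documents do not support that. As described, though, the ratings concern visual performance in a task; they are not the symptom record and do not mention dryness, burning or lens awareness.

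**Adverse event reporting.** Section 8.4 covers events seen by the investigator, volunteered by the subject or elicited by direct questioning, and section 8.3 counts a symptom as a possible event. So it is more than spontaneous reporting. The symptom form itself does not prompt by category, so it too depends largely on what the subject offers. But no direct questioning is scheduled after wear, and section 8.5 asks for the diagnosis rather than the symptom. This route does not feed the categorised table.

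**Unseen material.** The ocular symptoms procedure (Appendix E) is redacted, section 16.1 on questionnaires has no visible content, and the Manual of Procedures is not supplied. A post-wear symptom record in one of these cannot be excluded. Against that, the other post-wear repeats appear as numbered steps and this one does not.

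**The by-lens table is an inference.** Section 8.1 does not itself say by lens; section 9.1 says so in a general sentence that also covers baseline variables, and the table shells come from the sponsor and are not visible. That is fair. The literal reading leads to such a table, but nothing shows that the sponsor will produce it. If step 2 is meant as baseline only, the text still needs to say so.

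**Limited importance.** Symptoms carry no hypothesis and are absent from the endpoints and other observations in section 4.1. The study is an exploratory pilot with three to four hours of supervised wear and biomicroscopy after each removal. This limits the weight of the point but does not remove the mismatch.

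**Conclusion.** The mismatch is real. Sections 8.1 and 9.1 together call for symptoms to be tabulated by study lens type, while the visible schedule gives 0 of 40 exposures (0 of 50 with 25 subjects enrolled, all wearing both lenses) a scheduled symptom record on that lens. A table made from the scheduled records could not describe either study lens, and any carry-over would be credited to the wrong one.

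The conclusion assumes that the redacted and unsupplied material contains no post-wear symptom record, and that the general by-lens sentence in section 9.1 applies to ocular symptoms.

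Two stronger readings should be resisted. A reader might infer that the black ring is expected to cause blur or variable vision and that the plan would miss it; the documents say no such thing about the ring, and visual performance is measured and rated on the lens in other ways. A reader might also infer that the trial's main conclusion is at risk. It is not: the primary and secondary time-controlled acuity analyses do not use the symptom record. The effect is confined to one descriptive safety table, mainly its comfort categories. The change is still worth making, because symptoms on the lens cannot be recovered reliably once the visits are over.

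**What to change.** At Visits 2 and 3, repeat the symptom form after the vision assessments and before lens removal, between steps 13 and 14, worded for the lenses just worn. Add the same step to section 4.4.1. State in section 9.1 that this record is the one tabulated by study lens type, and that the step 2 record is a pre-insertion baseline not presented by lens type.

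The cost is one repeated form at each of two visits (assumed to be short) and a small protocol and eCRF amendment, with no extra visit or staff. It needs to be in place before the measurement visits begin.

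If the sponsor does not want the extra record, the minimum is to label the step 2 record as baseline only and remove it from the by-lens safety tables. That prevents a misleading table but leaves symptoms on the study lenses without a scheduled record. If the Manual of Procedures or a questionnaire already holds a post-wear symptom record, section 4.7.1 should cite it as a numbered step.

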4.8 DISCONTINUATION CRITERIA

Johnson & Johnson Vision Care, Inc. reserves the right to terminate the study at any time for any reason. Additionally, the IRB/IEC reserves the right to terminate the study if an unreasonable risk is determined. The study may be terminated by the Principal Investigator or Medical Monitor due to specific clinical observations, if in their opinion it would be unwise to continue.

Johnson & Johnson Vision Care, Inc. [and the IRB/IEC, if applicable] will evaluate all adverse events. If it is determined that an adverse event presents an unreasonable risk, the investigation, or that part of the investigation presenting the risk, will be terminated, as soon as possible.

Should the study be terminated (either prematurely or as scheduled), the Investigator will notify the Institutional Review Board (IRB), and Regulatory Authority as required by local regulatory requirements.

4.9 ACCOUNTABILITY PROCEDURES FOR INVESTIGATIONAL PRODUCT AND CONTROL

The Investigator will retain all lens shipment documentation for the test article accountability records.

Test articles must be kept in a locked storage cabinet, accessible only to those assigned by the Investigator for dispensing. All test articles must be accounted for. The Investigator may delegate this activity to an authorized study site staff member on the Delegation Log.

The Investigator will collect all unused test articles at the end of the subject's participation. Following final reconciliation of test articles, JJVCI will arrange for appropriate return or destruction of unused test articles.

Reference APPENDIX A: SITE INSTRUCTIONS FOR TEST ARTICLE RECEIPT AND TEST ARTICLE ACCOUNTABILITY for instructions on the Lens Depot.

4.10 PROCEDURES FOR MAINTAINING AND BREAKING RANDOMIZATION CODES

Subjects who have had their lens assignment unmasked are expected to return for all remaining scheduled evaluations. A replacement subject may be enrolled if a subject discontinues from the study prematurely (see section 5.1); the decision whether to enroll replacement subjects will be made by the joint agreement of the Investigator and Sponsor.

When dispensing test articles, the following steps should be followed to maintain randomization codes :

1. Investigator or designee (documented on the Delegation Log) will consult the randomization scheme to obtain the study test article assignment for that subject prior to dispensing.
2. Investigator or designee will record the subject's number on the appropriate line of the randomization scheme.
3. Investigator or designee will pull the appropriate test articles from the study supply. All test articles that were opened, whether dispensed or not, must be recorded on the Test Article Accountability Log in the "Dispensed" section.

There will be an un-masked investigator at the site, therefore no provision is required for breaking randomization codes.

4.11 REPORTING PRODUCT QUALITY COMPLAINTS

A Product Quality Complaint (PQC) refers to any written, electronic, or oral communication that alleges deficiencies related to the identity, quality, durability, reliability, safety, effectiveness or performance of test articles after they have been released for clinical trial use. A PQC is associated with any investigational product (i.e. product manufactured or supplied specifically for a clinical trial).

Complaint Handling

Once site personnel have become aware that a PQC has occurred, it shall then be recorded in the EDC system, which triggers an automatic email notification to the appropriate COM/CRA and Clinical QA representative. In cases where the EDC system in use is not configured to send automatic notifications, then the COM/CRA is responsible for notifying Clinical QA upon discovery that a PQC has occurred.

Upon receipt of the EDC notification the COM/CRA shall complete the applicable sections of the Product Quality Complaint Form [REDACTED]

For each complaint, the following minimum information shall be recorded by the CRA/COM on the Product Quality Complaint Form [REDACTED]

- Date the complaint was received/recorded in the EDC System (Date of Sponsor Awareness)
- Who received the complaint
- Study number
- Investigational site information (contact name, site ID, telephone number)
- Lot number(s)
- Unique Subject Identifier(s)
- Indication of who first observed complaint (site personnel or subject)
- OD/OS indication, along with whether or not the lens was inserted
- Any related AE number if applicable
- Detailed complaint description (scheduled/unscheduled visit, wear time, symptoms, resolution of symptoms, etc.)
- Eye Care Provider objective (slit lamp) findings if applicable
- Confirmation of product availability for return (and tracking information, if available), or rationale if product is not available for return [REDACTED]

Clinical QA will assign a unique number to the PQC. Complaint numbering is assigned as follows:

RDTC-XX-001, where RDTC = R&D Technical Complaint, XX = last two digits of the current year, 001 = sequential numbering starting with 001.

5.1 WITHDRAWAL CRITERIA

A subject will be withdrawn from the study for any of the following reasons:

- Lost to follow-up
- Withdrawal of consent
- Death
- Discontinuation of study treatment as a result of the investigator's clinical judgment that for safety reasons (e.g., adverse event) it is in the best interest of the subject to stop treatment.
- The subject becomes pregnant.

For discontinued subjects, the Investigator will:

- Update the enrollment log to document reason for discontinuation
- Complete the "last" Follow-up Visit form (scheduled or unscheduled)
- Complete the Final Evaluation form, indicating the reason that the subject was discontinued from the study
- Record the spherocylindrical refraction with best corrected distance visual acuity
- Collect used study lenses and test articles (worn or brought to the visit) from the subject and discard them
- Collect all unused study lenses and test articles from the subject

Subjects becoming pregnant during the study will be discontinued. Once discontinued, pregnant participants and their fetuses will not be monitored for study related purposes. At the Investigators' discretion, the study participant may be followed by the Investigator through delivery. However, this data will not be collected as part of the clinical study database. Pregnant participants are not discontinued from contact lens or solution related studies for safety concerns, but due to general concerns relating to pregnancy and contact lens use. Specifically, pregnant women are discontinued due to fluctuations in refractive error and/or visual acuity that occur secondary to systemic hormonal changes, and not due to unforeseen health risks to the mother or fetus.

In cases where a subject is lost to follow-up, every possible effort must be made to contact the subject and determine the reason for discontinuation / withdrawal. The measures taken to follow up must be documented including two written attempts and a certified letter as the final attempt.

